2 PROTOCOL SYNOPSIS

Title A Phase 3 Double-blind, Randomized, Placebo-controlled Study Evaluating the Efficacy and Safety of ELX/TEZ/IVA in Cystic Fibrosis Subjects 6 Years of Age

and Older With a Non-F508del ELX/TEZ/IVA-responsive CFTR Mutation

Brief Title Evaluation of Efficacy and Safety of ELX/TEZ/IVA in Subjects Without an

F508del Mutation

Clinical Phase and Clinical Study Type Phase 3 efficacy and safety

Objectives Primary Objective:

To evaluate the efficacy and pharmacodynamics (PD) of ELX/TEZ/IVA

Secondary Objective:

To evaluate safety and tolerability of ELX/TEZ/IVA

Endpoints Primary Endpoint:

 Absolute change from baseline in percent predicted forced expiratory volume in 1 second (ppFEV₁) through Week 24

Secondary Endpoints:

- Absolute change from baseline in sweat chloride (SwCl) through Week 24
- Absolute change from baseline in Cystic Fibrosis Questionnaire Revised (CFQ-R) respiratory domain (RD) score through Week 24
- Absolute change from baseline in body mass index (BMI) at Week 24
- Absolute change from baseline in weight at Week 24
- Number of pulmonary exacerbations (PEx) through Week 24
- Safety and tolerability assessments based on adverse events (AEs), clinical laboratory values, ECGs, vital signs, and pulse oximetry

Other Endpoints:

- Absolute change from baseline in BMI z-score (subjects ≤20 years of age) at Week 24
- Absolute change from baseline in weight z-score (subjects ≤20 years of age) at Week 24
- Plasma PK parameters including ELX, TEZ, IVA, and relevant metabolites

Number of Subjects Approximately 270 subjects will be enrolled in the study with up to approximately

30 subjects per *CFTR* mutation. Up to 10% of subjects may be enrolled with a

screening ppFEV₁ value >90% and ≤100% (approximately 27 subjects).

Study Population Male and female CF subjects 6 years of age and older with at least 1 non-F508del,

ELX/TEZ/IVA-responsive CFTR mutation

Investigational Drug Active substance: ELX (VX-445)/TEZ (VX-661)/IVA (VX-770)

Activity: ELX and TEZ are CFTR correctors; IVA is a CFTR potentiator **Strength and route of administration:** ELX/TEZ/IVA fixed-dose combination (FDC) tablets for oral administration at the following strengths:

- ELX 100 mg/TEZ 50 mg/IVA 75 mg
- ELX 50 mg/TEZ 25 mg/IVA 37.5 mg

Active substance: IVA (VX-770) Activity: CFTR potentiator

Strength and route of administration: IVA tablets for oral administration at the following strengths:

- IVA 150 mg
- IVA 75 mg

Study Duration

[figure not shown]
The total study duration is approximately 32 weeks (4 weeks for the Screening Period, 24 weeks for the Treatment Period, and 4 weeks for the Safety Follow-up Period).

Study Design

This is a Phase 3, randomized, placebo-controlled, double-blind, parallel group study. Subjects 6 years of age and older with a qualifying non-F508del ELX/TEZ/IVA-responsive CFTR mutation and no exclusionary mutations may be eligible for enrollment. Qualifying ELX/TEZ/IVA-responsive mutations can be categorized as minimal function (MF)-like and residual function (RF)-like. MF-like mutations have a clinical phenotype without evidence of residual CFTR function. RF-like mutations result in residual CFTR function. Exclusionary mutations are indicated for IVA in the EU label regardless of the mutation on the second allele.

Subjects will be randomized 2:1 (ELX/TEZ/IVA group: placebo group). Randomization will be stratified based on ppFEV₁ determined during the Screening Period (<70 versus ≥70), age at the Screening Visit (<18 years old versus ≥18 years old) and *CFTR* genotype (contains ≥1 RF-like mutation versus does not contain an RF-like mutation).

Figure 2-1 Study VX21-445-124 Design

The ELX/TEZ/IVA dose regimen will be based on the subject's age and weight on Day 1 as shown in Table 2-1; Subjects will receive this dose regimen throughout the Treatment Period, regardless of changes in age or weight.

Table 2-1 Treatment Period Dosages

Treatment Group Subject Age			
Weight	ELX Dosage	TEZ Dosage	IVA Dosage
ELX/TEZ/IVA			
≥12 years			
All weights	$200~\mathrm{mg}~\mathrm{qd}$	$100 \mathrm{\ mg\ qd}$	$150 \mathrm{\ mg\ q} 12\mathrm{h}$
≥6 to <12 years			
≥30 kg	200 mg qd	100 mg qd	$150 \mathrm{\ mg\ q} 12\mathrm{h}$
<30 kg	100 mg qd	50 mg qd	75 mg q12h
Placebo			
All ages and all weights	0 mg	0 mg	0 mg

ELX: elexacaftor; IVA: ivacaftor; q12h: every 12 hours; qd: once daily; TEZ: tezacaftor

ELX/TEZ/IVA will be administered as 2 FDC tablets in the morning and a single IVA monotherapy tablet in the evening regardless of dosing regimen.

Assessments

Efficacy and PD assessments: spirometry, CFQ-R, sweat chloride, weight, height, and PEx

Safety assessments: AEs, clinical laboratory assessments, ECGs, vital signs, pulse oximetry, physical examinations, and ophthalmologic examinations (for subjects <18 years of age on the date of informed consent)

PK assessments: Plasma PK concentrations of ELX, TEZ, IVA, and their relevant metabolites

Exploratory assessments: RNA, plasma and serum proteins

Statistical Analyses

The primary endpoint is the absolute change from baseline in ppFEV₁ through Week 24. The primary null hypothesis to be tested is that the mean absolute change from baseline in ppFEV₁ through Week 24 is the same for the ELX/TEZ/IVA and placebo treatment groups. The null hypothesis will be tested at a 2-sided significance level of 0.05.

Assuming a within-group SD of 9 percentage points and a 10% dropout rate at Week 24, a total sample size of 270 subjects (180 subjects in the ELX/TEZ/IVA group and 90 subjects in placebo group) will have approximately 90% power to detect a difference of 4.0 percentage points for the mean absolute change from baseline in ppFEV₁ through Week 24 between the 2 treatment groups, based on a 2-sided 2-sample t-test at a significance level of 0.05.

The primary analysis will be based on a mixed-effects model for repeated measures (MMRM). The model will include the absolute change from baseline in ppFEV₁ at Day 15, Week 4, Week 8, Week 16, and Week 24 as the dependent variable; treatment group, visit, and treatment-by-visit as fixed effects; additional covariates will be included as appropriate and details will be specified in the Statistical Analysis Plan (SAP); and an unstructured covariance structure will be used to model the within-subject errors.

The primary result obtained from the model will be the estimated treatment difference through Week 24. The adjusted mean with a 2-sided 95% CI and a 2-sided *P* value will be provided.

The safety endpoints include AEs, clinical laboratory values, ECGs, vital signs, and pulse oximetry through the Safety Follow-up Visit. The safety analysis will be descriptive only.

Independent Data Monitoring Committee

Safety and tolerability data will be reviewed by an independent data monitoring committee (IDMC) to ensure the safety of the subjects. Procedural details of the IDMC's structure and function, frequency of meetings, and data planned for review will be in the IDMC charter. The IDMC charter will be finalized before the first subject is screened.

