7.2 Secondary Endpoints

- Absolute change from baseline in SwCl through Week 24
- Absolute change from baseline in Cystic Fibrosis Questionnaire- Revised respiratory domain (CFQ-R RD) score through Week 24
- Absolute change from baseline in body mass index (BMI) at Week 24
- Absolute change from baseline in weight at Week 24
- Number of pulmonary exacerbations (PEx) through Week 24
- Safety and tolerability assessments based on AE, clinical laboratory values, ECGs, vital signs, and pulse oximetry

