9.3.1.2 Primary Analysis

The primary analysis will be performed using a MMRM with change from baseline at Day 15, Week 4, Week 8, Week 16, and Week 24 as the dependent variable. The model will include treatment group, visit, and treatment by visit interaction as fixed effects, with continuous baseline ppFEV₁, age at screening (<18 versus \geq 18 years of age) and mutation group (contains \geq 1 RF-like mutation versus does not contain an RF-like mutation) as covariates. The model will be estimated using restricted maximum likelihood. Denominator degrees of freedom for the *F*-test for fixed effects will be estimated using the Kenward-Roger approximation². An unstructured covariance structure will be used to model the within-subject errors. If the model estimation does not converge, a compound symmetry covariance structure will be used instead. Conditional on the observed data and covariates, missing data will be assumed to be missing at random.

The primary result obtained from the model will be the estimated treatment difference through Week 24, defined as the averaged treatment effects estimated at Week 4, Week 8, Week 16, and Week 24. The adjusted means with 2-sided 95% CIs and 2-sided *P* value will be provided. Furthermore, the treatment difference at each post-baseline visit obtained from the model will also be provided.

The estimated within group change from baseline and treatment difference at each post-baseline visit, obtained from the model, will be provided. The estimated within group change and its SE at each post-baseline visit will also be plotted by treatment group. In addition, the post-baseline raw values and the absolute change from baseline at each post-baseline visit will be summarized descriptively (n, mean, SD, median, minimum, and maximum).

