9.3.2.2 Analysis Method

Absolute change in SwCl from baseline through Week 24: The analysis of absolute change from baseline in SwCl through Week 24 will be based on an MMRM similar to the analysis of the primary endpoint above, with absolute change from baseline in SwCl at Day 15, Week 4, Week 8, Week 16, and Week 24 as the dependent variable.

The primary result obtained from the model will be the estimated treatment difference through Week 24, defined as the averaged treatment effects estimated at Week 4, Week 8, Week 16, and Week 24. The adjusted mean with a 2-sided 95% CI and a 2-sided *P* value will be provided.

The estimated within group change from baseline and treatment difference at each post-baseline visit, obtained from the model, will be provided. The estimated within group change and its SE at each post-baseline visit will also be plotted by treatment group. In addition, the post-baseline raw values and the absolute change from baseline at each post-baseline visit will be summarized descriptively (n, mean, SD, median, minimum, and maximum).

Absolute change from baseline in CFQ-R Respiratory Domain (RD) score through Week 24: Analysis of this domain will be based on an MMRM similar to the analysis of the primary efficacy variable. Data obtained from Week 4, Week 8, Week 16, and Week 24 Visits will be included in the model to estimate the treatment effect through Week 24. Plot and summary tables similar to those for ppFEV₁ and SwCl will be provided.

Absolute change from baseline in BMI at Week 24: Analysis of this variable will be based on an MMRM similar to the analysis of the primary efficacy variable. Data obtained from Day 15, Week 4, Week 8, Week 16, and Week 24 Visits will be included in the model. Plot and summary tables similar to those for ppFEV₁ and SwCl will be provided.

Absolute change from baseline in weight at Week 24: Analysis of this variable will be based on an MMRM similar to the analysis of the primary efficacy variable. Data obtained from Day 15, Week 4, Week 8, Week 16, and Week 24 Visits will be included in the model. Plot and summary tables similar to those for ppFEV₁ and SwCl will be provided.

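### The weight and BMI models allow one child–adult difference for all five visits, so the Week 24 standard error is somewhat too large: about 1–6% for weight on moderate assumptions

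*Protocol*

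**What the plan says.** For ppFEV₁, the protocol synopsis lists "treatment group, visit, and treatment-by-visit as fixed effects; additional covariates will be included as appropriate", with the details left to the SAP.

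SAP 9.3.1.2 fixes the primary MMRM: "The model will include treatment group, visit, and treatment by visit interaction as fixed effects, with continuous baseline ppFEV₁, age at screening" in two groups and mutation group as covariates. Treatment is the only factor crossed with visit. The covariance is unstructured, with compound symmetry if the model does not converge.

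For both weight and BMI, SAP 9.3.2.2 says: "Analysis of this variable will be based on an MMRM similar to the analysis of the primary efficacy variable". The visits are Day 15 and Weeks 4, 8, 16 and 24. No covariate-by-visit term is written. The section also does not say whether baseline weight or BMI replaces baseline ppFEV₁.

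The endpoint is raw weight: "Absolute change from baseline in weight at Week 24" (Protocol 7.2). Subjects aged 6 and over are eligible (Protocol 8.1), and one randomisation stratum is "age at the Screening Visit (<18 years old versus ≥18 years old" (Protocol synopsis; also SAP 7.3). In SAP 9.3.2.3, BMI and weight are the third and fourth secondary tests, ahead of pulmonary exacerbations. Growth-adjusted z-scores are analysed only in subjects aged 20 or younger, as other endpoints outside the hierarchy (SAP 9.3.3.2).

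**The concern.** Read as written, the model fits the same child–adult difference in weight change at Day 15 and at Week 24. In growing children that difference starts near zero and accumulates. Under an unstructured covariance the single age coefficient is weighted towards the early visits, where weight change varies least. At Week 24, the only visit tested for these endpoints, the model then hardly adjusts for age.

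The unadjusted gap goes into the Week 24 residual variance and from there into the standard error. Age-stratified randomisation balances age between the arms, so the gap cancels from the treatment difference itself. The reported interval is therefore wider than it need be and the test runs below its nominal 5%. A miss on BMI or weight stops formal testing of everything after it in the hierarchy, so avoidable loss of power at these two steps deserves attention.

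**Working it through.** **The plan's own figure.** The only power statement is for ppFEV₁ (Protocol 12.1): 270 subjects, SD 9, difference 4.0, 10% dropout. With 162 v 81 completers, SE = 9 × √(1/162 + 1/81) = 1.225, and power = Φ(4/1.225 − 1.960) = 90.4%. It reproduces, but it says nothing about weight or BMI, for which no figure is given.

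**Inputs from the documents.** 180 v 90 subjects; five visits; two-sided 0.05; age as a randomisation stratum and a main-effect covariate.

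**Inputs assumed, because the documents give none.** Share of children p; extra gain of children over adults by Week 24, D, accruing linearly; Week 24 within-age-group SD. Residuals are a random walk plus measurement error (error SD 0.5 kg in the rows with SD 2.5 and 2.0, 0.7 kg with SD 3.0; for BMI 0.3 and 0.25 kg/m²). Data are complete.

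**Formulas.** Let g be the vector of true age gaps over the visits.
- Fitted constant age effect: c = (1′V⁻¹g)/(1′V⁻¹1), where V is the true covariance plus p(1 − p)(g − c)(g − c)′.
- Correct Week 24 SE: SD × √(1/180 + 1/90) = 0.1291 × SD.
- SE ratio, model as written to model with age-by-visit: r = √[1 + p(1 − p)(D − c)²/SD²].

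**One case in full.** p = 0.4, D = 2 kg, SD = 2.5 kg give c = 0.23 kg, so about 1.77 of the 2 kg is left in the residual. r = √(1 + 0.24 × 1.77²/6.25) = √1.12 = 1.06. SE is 0.342 against 0.1291 × 2.5 = 0.323 kg.

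| Endpoint | Children | D | SD | c | SE as written | SE with age-by-visit | Excess |
|---|---|---|---|---|---|---|---|
| Weight, kg | 10% | 1 | 3.0 | 0.12 | 0.389 | 0.387 | 0.4% |
| Weight | 20% | 1 | 3.0 | 0.12 | 0.390 | 0.387 | 0.7% |
| Weight | 10% | 2 | 2.5 | 0.23 | 0.330 | 0.323 | 2.2% |
| Weight | 30% | 1.5 | 3.0 | 0.19 | 0.395 | 0.387 | 2.0% |
| Weight | 30% | 2 | 2.5 | 0.23 | 0.339 | 0.323 | 5.1% |
| Weight | 40% | 2 | 2.5 | 0.23 | 0.342 | 0.323 | 5.9% |
| Weight, extreme | 50% | 3 | 2.0 | 0.38 | 0.309 | 0.258 | 19.5% |
| BMI, kg/m² | 30% | 0.3 | 1.0 | 0.04 | 0.130 | 0.129 | 0.7% |
| BMI | 50% | 0.5 | 0.8 | 0.07 | 0.107 | 0.103 | 3.5% |

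If D = 0, then r = 1.

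**Check by simulation.** Simulated trials of 270 subjects, fitted with and without age-by-visit, agree. At 40%, 2 kg and SD 2.5 the SEs were 0.343 and 0.323, the empirical SD of the estimate was 0.324 under both models, and type I error was 3.8% v 4.9%. The mean estimate was essentially zero under the null.

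**Consequence.** The true sampling SD is unchanged, so type I error is 2[1 − Φ(1.960r)] and a test with 80% power under the better model has power Φ(1.960 + 0.842 − 1.960r). For r = 1.02 these are 4.6% and 79%; for r = 1.06, 3.8% and 77%. At r = 1.06 the interval is as wide as one from 11% fewer subjects (1 − 1/1.06² = 0.11).

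**The case against.** Several points on the other side stand.

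- The synopsis sentence concerns ppFEV₁ and defers covariates. The decisive text is SAP 9.3.1.2 and 9.3.2.2. Even there, a similar model is not necessarily an identical one, so the main-effect-only reading is the natural one but still an inference.
- The size rests wholly on assumed inputs. No minimum share of children is set, and the under-18 group includes older adolescents, so an average extra gain of 2–3 kg has no support in the documents.
- The size also depends on the covariance. For 40%, 2 kg and SD 2.5, more measurement error raises c to about 0.50 kg and cuts the excess to 4.2%. With equal variance at all visits c is 0.90 kg and the excess is 2.3%.
- A separate set of simulated trials gave type I error of 3.0–3.6% for the model as written at gaps of 1.5–2 kg, but 4.0% for the model with age-by-visit on the same data. Not all of the shortfall from 5% there comes from the missing term.

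A reader might infer that the weight and BMI results would be biased or their tests invalid. They would not: age is balanced by design, the estimate is unbiased and the error is conservative. A reader might also infer that the primary model shares the fault. The documents do not support that: ppFEV₁ is already standardised for age, sex and height, and no problem has been shown for it or for the other MMRMs.

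**Conclusion.** The point holds as a modest, avoidable loss of efficiency. If the child–adult gap in weight change widens over the visits, the Week 24 standard error from the model as written is too large. With 10–40% children, 1–2 kg extra gain and SD 2.5–3 kg, the excess for weight is roughly 1–6% (0.4% at the smallest corner). For BMI it is about 1–3.5%. About 20% arises only when 50% children, 3 kg and SD 2 kg are taken together, and should not be quoted as typical. With no growth gap there is no effect. Dropout was not modelled.

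One might go on to conclude that the hierarchy is likely to fail at weight and block the exacerbation test. The plan states no expected effect or power for weight or BMI, so that cannot be shown. What can be said is that a case starting at 80% power would lose about 1 to 3 points (r = 1.02 to 1.06).

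**What to change.** Before data lock, state in SAP 9.3.2.2 that the weight and BMI MMRMs include age group-by-visit in addition to treatment-by-visit. The primary ppFEV₁ model and the other MMRMs need not change on this ground.

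The cost is one sentence in a SAP amendment, which SAP Section 4 allows before data lock, and four extra parameters in each of two models with about 270 subjects. No new data are needed and the Week 24 treatment contrast keeps its meaning. It should be written before unblinding, because adding the term afterwards would be a data-dependent choice on a formally tested endpoint.

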3 SCHEDULE OF ASSESSMENTS

Schedules of assessments are in Table 3-1 and Table 3-2.

Table 3-1 Study VX21-445-124: Screening

	Screening Visit ^a	
Event/Assessment	Day -28 to Day -1	Comments
Informed consent (and assent, if applicable)	X	
Demographics	X	Section 11.1
Medical history	X	Section 11.1
CFTR genotype	X	Performed for all subjects (Section 11.5.2). A subject's screening CFTR genotype must confirm eligibility before the subject is randomized.
Medications review	X	Information regarding medications taken within 56 days before the Screening Visit will be collected; Section 9.5.
Height, weight, and BMI	X	Weight and height will be measured with shoes off; Sections 11.4.4 and 11.5.3
Full physical examination	X	Section 11.5.3
Vital signs and pulse oximetry	X	Collected after the subject has been at rest for at least 5 minutes; Section 11.5.3
Standard 12-lead ECG	X	Performed prior to any procedure that may affect heart rate (e.g., blood draws) and after subject has been at rest for at least 5 minutes; Section 11.5.4
Serum FSH	X	Suspected postmenopausal female subjects only; Section 11.5.2
Serum pregnancy test	X	Female subjects 9 years of age and older, and female subjects who have undergone menarche (regardless of age), Section 11.5.2
Serum chemistry	X	Section 11.5.2
Hematology and coagulation	X	
Urinalysis	X	
Ophthalmological examination	X	Conducted by an ophthalmologist or optometrist for subjects <18 years of age on the date of initial informed consent; Section 11.5.5
Sweat chloride	X	Section 11.4.2
Spirometry	X	Performed pre- or post-bronchodilator; Section 11.4.1
Adverse events	Continuous from signing of informed consent form (ICF) through completion of study participation	Section 11.5.1

BMI: body mass index; *CFTR*: cystic fibrosis transmembrane conductance regulator gene; ECG: electrocardiogram; FSH: follicle-stimulating hormone

a Visit must be performed in clinic (Section 9.1.7)

Protocol VX21-445-124, Version 3.0 Page 8 of 62

Table 3-2 Study VX21-445-124: Treatment Period and Safety Follow-up Visit

Event/Assessment ^a	Day 1 ^b	Day 15 (± 3 Days)	Week 4 (± 5 Days)	Week 8 (± 5 Days)	Week 12 (± 5 Days)	Week 16 (± 5 Days)	Week 20 (± 5 Days)	Week 24 ^b (± 5 Days)	ETT Visit ^c	Safety Follow-up 28 (± 7) Days After Last Dose of Study Drug ^d	Comments
Clinic Visit	X	X	X	X		X		X	X	X	See Section 9.1.7 for use of remote measures in extenuating circumstances.
Telephone contact or telemedicine video conference					X		X				Assess subject's status, any AEs, concomitant medications, treatments, and procedures.
Randomization	X										Section 9.2
Safety, efficacy, and of	her asses	sments									
CFQ-R	X		X	X		X		X	X	Х	Completed before the start of any other assessments; Section 11.4.3
Weight and height	X	X	X	X		X		X	X	X	Measured with shoes off; Section 11.4.4
Vital signs and pulse oximetry	X	X	X	X		X		X	X	X	Performed after subject has rested for at least 5 minutes; Section 11.5.3
Standard 12-lead ECG	X	x	х	x		х		х	Х	х	Performed prior to any procedure that may affect heart rate (e.g., blood draws) and after subject has rested for at least 5 minutes; Section 11.5.4

a All assessments will be performed before dosing unless noted otherwise.

b These visits must be performed in clinic (Section 9.1.7).

^c If the subject prematurely discontinues study treatment, an ETT Visit should be scheduled as soon as possible after the decision to discontinue treatment. Subjects who prematurely discontinue treatment will continue to complete all scheduled study visits for assessments following completion of the ETT Visit.

d The Safety Follow-Up Visit is not required for subjects who complete the Week 24 Visit and enroll in an optional open-label extension safety study within 28 days after the last dose of study drug. If an ETT Visit occurs 3 weeks or later following the last dose of study drug, then the ETT Visit replaces the Safety Follow-up Visit.

Protocol VX21-445-124, Version 3.0 Page 9 of 62

Table 3-2 Study VX21-445-124: Treatment Period and Safety Follow-up Visit

	Day	Day 15	Week 4	Week 8	Week 12	Week 16	Week 20	Week 24 ^b	ЕТТ	Safety Follow-up 28 (± 7) Days After Last Dose of	
Event/Assessment ^a	1 ^b	(± 3 Days)	(± 5 Days)	(± 5 Days)	(± 5 Days)	(± 5 Days)	(± 5 Days)	(± 5 Days)	Visit ^c	Study Drug ^d	Comments
Physical examination	Full							Full	Full		Symptom-directed physical examinations may occur at any time if deemed necessary by the investigator; Section 11.5.3
Ophthalmological examination								X at or up to 4 weeks before	X		Conducted by an ophthalmologist or optometrist for subjects <18 years of age on the date of informed consent; Section 11.5.5
Pregnancy test (female subjects of childbearing potential)	urine	serum or urine	serum or urine	serum or urine	urine (at home)	serum or urine	urine (at home)	serum or urine	serum or urine	serum or urine	Female subjects of childbearing potential are defined in Section 11.5.6.1.
Serum chemistry	X	X	X	X		X		X	X	X	Collected before the
Hematology	X	X	X	X		X		X	X	X	first dose of study drug on Day 1; Section
Coagulation	X							X	X	X	11.5.2
PK sampling	X		X					X			Collected within 60 min before the AM dose; Section 11.2.1
Urinalysis	X							X	X	X	Section 11.5.2

Protocol VX21-445-124, Version 3.0

Table 3-2 Study VX21-445-124: Treatment Period and Safety Follow-up Visit

Event/Assessment ^a	Day 1 ^b	Day 15 (± 3 Days)	Week 4 (± 5 Days)	Week 8 (± 5 Days)	Week 12 (± 5 Days)	Week 16 (± 5 Days)	Week 20 (± 5 Days)	Week 24 ^b (± 5 Days)	ETT Visit ^e	Safety Follow-up 28 (± 7) Days After Last Dose of Study Drug ^d	Comments
Spirometry	x	х	x	x		х		х	х	х	Performed before study drug dosing. Should be performed pre-bronchodilator at approximately the same time at each visit (Section 11.4.1). If the visit is performed as a home health visit, spirometry may be performed using a mobile device (Section 9.1.7)
Sweat chloride	X	X	X	X		X		X			Section 11.4.2
Blood sample for exploratory RNA and protein analysis	X					X					Subjects weighing ≥22 kg at screening only. Section 11.3
Adverse events			Conti	nuous from sig	ning of ICF th	ough completion	on of study par	ticipation			Section 11.5.1
Other events related to outcome			Conti	nuous from sig	ning of ICF th	rough completion	on of study par	ticipation			Section 11.4.5
Medications review			Conti	nuous from sig	ning of ICF th	ough completion	on of study par	ticipation			Section 9.5
Non-pharmacological treatment and procedures review			Conti	nuous from sig	ming of ICF th	rough completion	on of study par	ticipation			
Study drug administra	tion										
Study drug dosing			Day		ning before We	ek 24 Visit					Section 9.6
Study drug compliance review	X	X	X	X	X	X	X	X	X	X	Section 10.6.

CFQ-R: Cystic Fibrosis Questionnaire-Revised; ECG: electrocardiogram; ETT: Early Termination of Treatment; ICF: informed consent form; PK: pharmacokinetic(s); RNA: ribonucleic acid

